LIGHT THERAPY FOR THE TREATMENT OF MS-ASSOCIATED FATIGUE

Protocol

NCT03060759

August 8, 2018

Light Therapy for Multiple Sclerosis Fatigue
Detailed Protocol; version 3

I. BACKGROUND AND SIGNIFICANCE:

Historical background, rationale behind the proposed research, and potential benefits to patients and/or society.

Fatigue is the most commonly reported symptom among people living with multiple sclerosis (pMS).¹⁻⁴ More than a quarter of pMS state fatigue is their most disabling symptom.⁵ Despite the impact of fatigue in MS, there are few effective treatment options. Many pMS seek non-pharmacological options for their symptoms but have limited evidence upon which to make important treatment decisions.

Fatigue may have multiple mechanisms in MS including dysfunction of the dopaminergic neurons in the basal ganglia,^{6,7} endocrine dysfunction due to suppression of the hypothalamic pituitary adrenal axis,⁸ cytokine induction in a continuous, pro-inflammatory state of the brain,⁹ and/or reduced function of the frontal cortices.⁶ We hypothesize that supplemental exposure to bright white light will be associated with a reduction in MS-associated fatigue. In a prospective study following pMS, self-reported sunlight exposure was correlated with lower levels of fatigue.¹⁰ Although causality cannot be determined from that study, this suggests a possible therapeutic benefit of light for fatigue in pMS. Light therapy has also been associated with reduction of fatigue in other neurological and medical disorders including Parkinson's disease¹¹, traumatic brain injury¹², seasonal affective disorder¹³ and cancer-related fatigue¹⁴. If mechanisms of fatigue are overlapping across disorders in which bright LT has shown therapeutic benefits, LT may be an unrecognized therapeutic option for fatigue among pMS. The beneficial effects of light on fatigue may be mediated through its direct alerting effects or through its effects as the main synchronizer of the circadian system.

II. SPECIFIC AIMS

Objectives and hypotheses to be tested:

1. To determine whether bright white light (BWL) (active condition) compared to dim red light (DRL) (control condition) will reduce self-reported fatigue among pMS when administered twice daily in one-hour sessions for four consecutive weeks.

Hypothesis 1: Bright white LT will reduce the average self-reported fatigue score on the Fatigue Severity Score (FSS) by ≥ 10 points among pMS with fatigue, compared to pMS treated with dim red LT.

2. To determine the feasibility and tolerability of LT as an intervention strategy to reduce fatigue in pMS by reporting the adherence data with the study intervention and participant-reported side effects.

Hypothesis 2: LT will be both feasible and well-tolerated in pMS.

III. SUBJECT SELECTION:

A. Inclusion/Exclusion Criteria:

a. *Inclusion Criteria:* (1) relapsing remitting or secondary

progressive MS based on McDonald Criteria (2010)¹⁵ (2) ≥ 18 and ≤ 70 years old, (3) presence of fatigue defined as FSS ≥ 36 on screening (range 7-63 possible points).¹⁶

- b. *Exclusion criteria:* (1) change in an anti-depressant, (2) fatigue medication regimen, or MS disease modifying therapy up to 4 weeks prior to study screening, (3) Beck Depression Inventory II score >20 , (4) shift work, (5) use of photosensitizing medication, (6) presence of eye trauma or acute optic neuritis within the preceding 3 months or presence of macular degeneration or other retinal disease, (7) history of traumatic brain injury or (8) probable (untreated) sleep apnea based on Berlin questionnaire (9) significant anemia (10) history of mania, (11) MS relapse in the preceding four weeks, (12) current pregnancy, (13) known photosensitivity (14) other complicating illness preventing study completion. Patients will be withdrawn from study participation if they experience a clinical relapse requiring hospitalization or treatment with steroids during the study period. They will also be withdrawn if there is a change in disease modifying therapy for MS, depression or fatigue during the study period.

B. Subject Recruitment:

Participants will be recruited from the MS Clinic at Massachusetts General Hospital (MGH). 700 pMS are followed in this clinic. In preliminary screening, $\sim 2/3$ of MS patients at MGH have a FSS ≥ 36 (mean 45.9, standard deviation 15.2 points) and will be eligible for participation. We will use flyers placed throughout the hospital as well as letters to eligible patients in order to assist with recruitment. We will use MGH's Research Subject Volunteer Program (RSVP), a participant matching service, to identify subjects with enthusiasm for the project. If the participant is a patient of the principal investigator, a research physician or study coordinator will explain the study so they do not feel obligated to participate. Subjects between 18-70 years old will be recruited for they study. For older subjects, best clinical judgment will be used to determine if participation is feasible.

IV. SUBJECT ENROLLMENT:

- A. **Methods of enrollment, procedures for obtaining informed consent, and randomization:** Following a redcap screening survey (Beck Depression Inventory, Fatigue Severity Scale, Berlin Questionnaire, Inclusion/exclusion criteria) and a baseline visit, eligible participants will be consented and randomized using a computer-based randomization generator 1:1 to (a) white LT (10,000 lux), or (b) dim red LT (<300 lux). Dim red LT is a widely accepted controlled condition in clinical studies of LT. In attempt to reduce placebo effect, the participants will be informed that this study will examine the effect of two different light spectra on fatigue and that one will be placebo. They will be informed that they will not know the

group they are in. Informed written consent will be obtained at the time of enrollment at the screening/baseline visit.

V. STUDY PROCEDURES:

A. Study visits and parameters to be measured, data to be collected and when the data is to be collected:

Interested patients will be identified through the MS clinic at MGH, the RSVP, the Partners Clinical Trials website or alerted by flyer/letter. Following a phone call to explain the details and requirements of the study, interested participants will undergo a screening survey administered through redcap, link sent by email. This survey will include questions regarding the inclusion/exclusion criteria, the Fatigue Severity Scale (≥ 36), the Beck Depression Inventory (≤ 20), and the Berlin Questionnaire to screen the participant for eligibility. Participants who are eligible and remain willing to participate will then be scheduled for an in-person visit with either the principal investigator (PI) or another physician involved in the study for a baseline visit. The following assessments will be administered by the study PI/research physician at the baseline visit: (1) the Kurtzke Extended Disability Status Scale (EDSS), (2) FSS, (3) Pittsburg Sleep Quality Index (PSQI), (4) Epworth Sleepiness Scale (ESS), (5) Multiple Sclerosis Quality of Life-54 (MSQOL-54). Additionally data will be obtained from patient report and chart review on the patient's history of RRMS or SPMS including time from diagnosis, disease modifying therapy, baseline neurologic symptoms, imaging features such as presence or absence of spinal cord lesions as well as data on medical comorbidities and medications used. Data on the use of caffeine, alcohol and tobacco will also be collected. The participants most recent Vitamin D level will also be obtained from their medical record. This will be collected in order to assess whether response to light therapy differs amongst patients with differing levels of vitamin D deficiency. Studies in patients with MS fatigue show mixed results regarding the relationship of fatigue with vitamin D level and supplementation ¹⁹⁻²¹.

At the baseline visit, participants will be randomized to BWL or DRL. The research coordinator will be aware of the assignment and will distribute the appropriate light therapy boxes during the visit. The PI and research physician will be blinded to treatment assignment so as not to bias follow-up visit assessments. The group assignments will be kept in an excel file that only the research coordinator has access to to maintain blindedness.

After randomization the subjects will begin the study period. The study period will include a 2-week baseline period without any light therapy treatment, a four week treatment period and a four week follow-up (wash-out) period. Throughout the study period, participants will record their fatigue using the Visual Analogue Fatigue Scale (VAFS) four times daily, starting after waking up, and

every four hours thereafter (at least 3x per day). The VAFS is a simple, validated 10-point scale ranging from 1 to 10 in which participants can report their fatigue as a snapshot at that particular moment.¹⁸ Data collection will occur by participants in self-report fashion on paper that will be returned to the study staff at the end of the study period. During the entirety of the study period including baseline and wash-out, patients will also collect a sleep diary which requires filling out once per day (<1 minute). During the four week treatment period patients will record their use of light therapy in a log as well as any side effects they are experiencing. Patients will be instructed to sit in front of the light box with eyes approximately 18.5 inches from the light source. They will use the box for one hour twice per day, in the morning starting two hours after awakening and in the evening starting 3 hours before bedtime. Eyes should be open while using LT but patients do not have to look directly at the light and can eat, read, watch television etc. during use.

There will be two visits with the principal investigator (PI) including the baseline visit described above, a visit with the PI at the end of the treatment period in which participants will perform a FSS, MSQOL-54 and discuss their experiences with LT. Final follow up surveys (FSS and MSQOL54) will be sent using redcap by email following the 4-week washout period. Patients will be reminded not to reveal their treatment assignment to the examining blinded physician.

- B. Device to be used:** The light box used for LT (SunRay by *The Sunbox Company*, Gaithersburg, Maryland, USA) is approximately 15.5" tall x 23" wide x 3.25" deep and is designed to stand on a desk or tabletop. It can be used both in the home or office. The light is delivered at a downward angle to maximize the effectiveness. The box runs on 124 watts and contains full spectrum 5000k 10,000 lux bulbs. Bright light treatment requires at least 2,500 lux to be effective.¹⁷

The lights are tested by the supply company before distribution to ensure they meet advertised levels of lux output. Lights are turned on by the study team to make sure they work before being provided to study participants. In cases where bulbs burn out, they are replaced with new bulbs purchased from the same supply company.

VI. BIostatistical Analysis:
Specific data variables, study endpoints, statistical methods, power analysis

The primary outcome measure will be change in the average FSS after

the 4-week study period in the bright light “active” versus the dim light “control” groups. There are no available data on FSS in response to bright LT in pMS. To test the specific aim of change of ≥ 15 points, we used the conventional values of $\alpha=0.05$ and $\beta=0.80$ for 2-tailed tests of probability with equally sized groups. For a difference in ≥ 15 points, with an estimated standard deviation of 15.2 points and mean of 45.9 points from preliminary data collection at the MGH MS Clinic, we require a minimum of 15 people in either group. The primary aim will compare the mean change in FSS scores before initiation and after completion of LT, in an intention to treat analysis comparing the active and control condition groups. The secondary outcome measure will be a change in the global VAFS scores after light therapy in both groups. Frequencies will be used to describe baseline characteristics across treatment arms. χ^2 statistics or Fisher’s exact test will be used to compare the differences between groups. VAFS will be evaluated using a mixed-effects model which accounts for correlation between repeated measurements. Participant logbooks will be used to generate summary statistics and to graphically display fatigue patterns throughout the day among pMS in both groups. Logbooks will also be used to qualitatively assess the safety and tolerability of LT.

RISKS AND DISCOMFORTS:

Device complications/malfunctions and Psychosocial (non-medical risks)

We anticipate light therapy to be well-tolerated. Potential side effects of light therapy include triggering photosensitivity in those prone to migraines as well as triggering mania in those with a history of mania (mania is an exclusion criteria to trial participation). Patients may find it burdensome to devote two hours per day to light therapy but may also be motivated to try this potential treatment for a disorder with minimal current treatment options. Patients may also find the frequent VAFS tracking burdensome although this has been used successfully in the past in trials of light therapy in Parkinson’s disease patients¹¹. We do not anticipate device malfunction to lead to any risks or safety issues. Should the device stop working, participants will be given instructions on how to contact the research team to obtain a new device.

VII. POTENTIAL BENEFITS

Potential benefits to participating individuals and to society

Participants may benefit by improvement of their fatigue severity with light therapy. Society and patients with MS stand to benefit if LT is found to be an effective, feasible, and tolerable non-pharmacologic therapy for a very common problem among MS patients for which there are currently limited treatment options. Data gathered from this study will be essential to inform a larger randomized study of LT for fatigue reduction in pMS in general or among subgroups of pMS with promising preliminary results.

VIII. MONITORING AND QUALITY ASSURANCE

- A. **Independent monitoring of source data:** If participants in the bright white LT do not self-administer the intervention, it may underestimate the effect of LT. Participants will be called two weeks after the commencement of the light therapy treatment phase by the research coordinator, including addressing challenges to completion of LT. Honest reporting of LT use will be encouraged.
- B. **Safety Monitoring:** As above, participants will be called two weeks after the commencement of the light therapy treatment phase to assess for tolerability problems with light therapy. They will be encouraged to contact the research team immediately to report any potential side effects of light therapy. The research coordinator will be available by phone during regular business hours, and the PI will be available to patients at all times by page.
- C. **Outcomes Monitoring:** Outcomes including therapy efficacy, tolerability and feasibility will be reviewed at each treatment visit.

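### Photosensitizing medication is excluded at entry, but no listed contact after the baseline visit asks about new medication, before or during light therapy

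*Combined protocol and SAP*

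**What the plan says.** Section III.A names "5) use of photosensitizing medication" as an exclusion, and lists known photosensitivity as a separate item. The same section gives the reasons for withdrawal during the study: a relapse needing hospital care or steroids, and certain therapy changes ("They will also be withdrawn if there is a change in disease modifying therapy for MS, depression or fatigue during the study period"). Photosensitizing drugs are not among them.

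Section V.A puts the eligibility questions in the screening survey. At the baseline visit, history is taken from patient report and the chart, "as well as data on medical comorbidities and medications used". Randomization and the handing out of light boxes take place at that visit. The timetable then follows: "The study period will include a 2-week baseline period without any light therapy treatment, a four week treatment period", and after that a four-week wash-out. The light schedule is "They will use the box for one hour twice per day".

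The later contacts have these stated contents:

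- During treatment, "patients will record their use of light therapy in a log as well as any side effects they are experiencing" (Section V.A).
- Two weeks into light, the coordinator calls about difficulties in completing the sessions, tolerability and possible adverse events (Sections VIII.A, VIII.B and VIII.D).
- At the end of treatment, "participants will perform a FSS, MSQOL-54 and discuss their experiences with LT" (Section V.A).
- Participants may report side effects to the team at any time (Sections VIII.B and VIII.D).

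**The concern.** By excluding the drug separately from known photosensitivity, the protocol treats taking it as a reason to keep someone away from the light, with or without a reaction. That check is made at screening and baseline, and all of the light comes at least two weeks later. Someone prescribed such a drug in the meantime for an unrelated reason has no side effect of light and no adverse event to report. The later steps would therefore not be expected to bring it up unless symptoms follow.

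What is at stake is unrecognised exposure to light on a drug that the protocol considers unsuitable. This matters mainly in the 10,000 lux arm, since the control light is below 300 lux. A second, smaller consequence is that the withdrawal rule for changes in MS, depression or fatigue therapy has no scheduled question behind it either.

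**Working it through.** The plan gives no figure on this point to reproduce. The check is of the calendar, and then of what a question would gain.

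**Calendar (Sections V.A and VIII).** Take the baseline visit as day 0.

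- Light starts on day 14 and ends on day 14 + 28 = 42.
- The call falls at about day 14 + 14 = 28.
- Scheduled light is 28 days × 2 h = 56 h at most.
- From baseline to the call is 28 days, and from the call to the end of light is 14 days.
- The end-of-treatment visit lists no medication question. On the text the absence therefore runs to day 14 + 28 + 28 = 70, but exposure ends at day 42.

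**Assumptions for the gain.** The drug is started at a uniformly random time between day 0 and day 42. All scheduled light is taken. A question is answered correctly, and light stops on the day of the answer.

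**Case A: the drug is continued to the end of light.** Split the 42 days into thirds (days 0–14, 14–28 and 28–42).

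- As planned: a start before day 14 overlaps 28 days of light, and a later start overlaps 14 days on average. Mean = (1/3)(28) + (2/3)(14) = 18.67 days = 37.3 h.
- Question in the call: (14 + 7 + 7)/3 = 9.33 days = 18.7 h, which is 50% less. The maximum falls from 56 h to 14 × 2 = 28 h.
- Day-14 check as well: (0 + 7 + 7)/3 = 4.67 days = 9.3 h, which is 75% less. The maximum stays at 28 h.

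**Case B: a 7-day course.**

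- As planned: mean overlap with light = 7 × 28/42 = 4.67 days = 9.3 h.
- Question in the call: it helps only those on the drug on day 28, that is, starts on days 21–28. Light days removed, summed over start times, are 7²/2 = 24.5, so the mean removed is 24.5/42 = 0.58 days = 1.2 h. That is 0.58/4.67 = 12.5%.
- Day-14 check as well: it removes the same amount again, for 25% in total.

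**Number affected.** The documents give no rate of starting such a drug. If 1%, 2% or 5% did so in 42 days (assumed), the expected number among the 15 bright-arm participants of Section VI would be 0.15, 0.30 or 0.75. These are exposures, not injuries.

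**The case against.** The strongest case against is that this argues from silence. The protocol gives the purposes of the call but not its script, and the consent pages, which may tell participants to report new drugs, are not in this text. The withdrawal rule implies that some therapy changes are meant to be tracked. The photosensitizer item is also an entry criterion, and the sponsor did not make it a reason for withdrawal. These points stand as limits. They do not supply a medication question at any listed contact, and a voluntary report is not a scheduled check.

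A reader might infer that nothing at all is scheduled to detect a problem for 42 days. The documents do not support that. The log, the day-28 call with its adverse-event review, and open access to the team are real safety steps that could reveal a reaction or prompt someone to mention a new drug. What is absent is narrower: a question about medication. Nor is day 42 a point of detection. It is simply when light ends.

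A reader might also take the halving of undetected light as a general result. It holds only for a drug continued to the end of light, and for a short course the gain is much smaller. New eye events are not part of this gap, because symptoms and eye problems already have a route through adverse-event reporting and physician judgement.

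**Conclusion.** The point holds as a low-severity safety improvement. After baseline, no listed contact asks about new or changed medication. Unless a new photosensitizing drug happens to be one of the therapies in the withdrawal rule, the plan as written triggers no action for it. A participant without symptoms could receive up to 56 h of scheduled light unrecognised.

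Under the assumptions in the working, the call question cuts mean undetected light by about 50% if the drug is continued to the end of light, and by about 12.5% for a 7-day course. The true duration of use and rate of starting are unknown.

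Two stronger conclusions should not be drawn. The documents show no injury and give nothing from which to size one. They also give no basis for sizing any effect on the primary FSS comparison. Confidence is medium, because the consent text and call script might already cover this.

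**What to change.** Make four small changes to the protocol text.

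1. At the baseline visit, tell participants to report any new medication at once.
2. Add one question on new or changed medication to the existing two-week call. This also gives the withdrawal rule for MS, depression and fatigue therapy a scheduled check.
3. If a photosensitizing drug is reported, pause light in either arm until a study physician has reviewed it. The coordinator, who knows the assignment, passes on only the drug name. Pausing in the bright arm alone would reveal the arm, against the stated aim: "The PI and research physician will be blinded to treatment assignment so as not to bias follow-up visit assessments".
4. Keep collecting the FSS on schedule for anyone paused, so that they stay in the intention-to-treat comparison of Section VI.

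A brief REDCap medication check on the day light starts is optional. It would add about 30 short contacts (15 per group × 2). No extra eye questions are needed.

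The core change costs a few sentences and one question in a call that is already made. The downside is slightly less light delivered in a few participants, and possibly more withdrawals as therapy changes that the existing rule already covers come to light.

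### Patients withdrawn after randomisation but before the end of treatment have no scheduled primary FSS, and the intention-to-treat analysis does not say how to include them

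*Combined protocol and SAP*

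**What the plan says.** Section III.A gives two rules for leaving the study. The first is for relapse: "Patients will be withdrawn from study participation if they experience a clinical relapse requiring hospitalization or treatment with steroids during the study period". The second is for treatment changes: "They will also be withdrawn if there is a change in disease modifying therapy for MS, depression or fatigue during the study period".

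Section V.A randomises patients at the baseline visit, where the research coordinator "will distribute the appropriate light therapy boxes during the visit". It continues: "After randomization the subjects will begin the study period", and that period "will include a 2-week baseline period without any light therapy treatment, a four week treatment period and a four week follow-up (wash-out) period".

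After baseline, FSS is scheduled twice. One is in person, at "a visit with the PI at the end of the treatment period in which participants will perform a FSS, MSQOL-54"; the other is an emailed REDCap survey after wash-out.

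Section VI makes the primary comparison the mean FSS change from before light therapy starts to after it is completed, between arms, by intention to treat. It names a mixed-effects model for the secondary fatigue scale (VAFS) only. For FSS it states no model, no imputation and no sensitivity analysis for missing scores. The sample size is a minimum of 15 per group, with no stated allowance for loss.

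**The concern.** Every patient withdrawn under Section III has already been randomised and so belongs to the intention-to-treat population. If withdrawal comes before the end-of-treatment visit, the second score is not scheduled and a change cannot be computed. The withdrawal rule and the promised analysis therefore do not fit together.

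The reasons for loss matter. A patient whose fatigue is not improving may change fatigue or depression medication, and a relapse may itself affect fatigue. Losing poor responders from the dim red arm would understate the effect of light; losing them from the bright arm would overstate it. With about 15 per arm each score carries weight, and Section VII says the data are meant to inform a larger randomised study.

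**Working it through.** **1. Timeline.** Randomisation at baseline, then 2 + 4 + 4 = 10 weeks. The end-of-treatment FSS falls at 2 + 4 = 6 weeks.

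| Withdrawn in | FSS at end of treatment | FSS after wash-out |
|---|---|---|
| Weeks 1–2 (no light) | not scheduled | not scheduled |
| Weeks 3–6 (treatment) | not scheduled | not scheduled |
| Weeks 7–10 (wash-out) | already taken | lost |

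The primary endpoint is exposed in the first six weeks only. The documents describe no early-termination visit, no FSS at withdrawal and no follow-up afterwards.

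**2. The plan's own figure.** Section VI: difference 15, SD 15.2, two-sided alpha 0.05, power 0.80 (labelled beta in the text). The normal formula gives n = 2 × [(1.960 + 0.842) × 15.2/15]² = 16.1, so 17 per group; the t-test needs 18. The stated minimum of 15 gives t-test power of 74.2%. The point made here does not depend on this gap.

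**3. Range for the SD of change (assumed; the documents give none).** The clinic data are "mean 45.9, standard deviation 15.2 points", and entry requires "presence of fatigue defined as FSS ≥ 36 on screening (range 7-63 possible points". Scores limited to 36–63 cannot have an SD above 27/2 = 13.5 (about 14 as a sample SD at n = 15), so 15.2 cannot be the screening SD of enrolled patients. A normal distribution with mean 45.9 and SD 15.2, cut to 36–63, has SD 7.4. Then

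SD of change = √(s1² + s2² − 2·r·s1·s2)

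- s1 = 7.4, s2 = 7.4, r = 0.7: 5.7
- s1 = 7.4, s2 = 15.2, r = 0.3: 14.8

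The range used is 5.7 to 15.2, with the top extended to the planning SD.

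**4. Possible bias.** Assume 15 per arm, normal changes and losses from one arm only. If the k worst responders are lost, that arm's mean shifts by (sum of the k largest expected order statistics) / (15 − k). For 15 standard normal values the three largest are 1.736, 1.248 and 0.948.

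| Lost from one arm | Shift in SD | Points at SD 5.7 | Points at SD 15.2 |
|---|---|---|---|
| Worst 1 | 1.736/14 = 0.12 | 0.7 | 1.9 |
| Worst 2 | 2.984/13 = 0.23 | 1.3 | 3.5 |
| Worst 3 | 3.932/12 = 0.33 | 1.9 | 5.0 |
| 2 at random from worst 7 | 0.12 | 0.7 | 1.9 |
| 2 unrelated to response | 0 on average | 0 | 0 |

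**5. Precision.** With SD 15.2 and a two-sided t-test, going from 15 v 15 to 13 v 15 lowers power from 74.2% to 70.8% for 15 points (Section VI) and from 41.3% to 38.7% for 10 points (Hypothesis 1).

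**The case against.** The plan is silent rather than self-contradictory. It commits to intention to treat, does not forbid collecting FSS after withdrawal, and nowhere prescribes a completers-only analysis. Consent pages are not available, so wording there on data after withdrawal cannot be seen. All of this is true, but Section V gives no procedure for obtaining the score and Section VI no rule for its absence, whatever the consent form says.

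The number affected is unknown. The window is six weeks, and entry requires four weeks without relapse or a relevant treatment change. Losses in the two weeks before light are unlikely to depend on arm; they could do so only because the boxes have already been handed out. These limits on how often it happens stand.

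The two-worst case is extreme. The standard error of the difference at 15 v 15 is √(2/15) = 0.365 SD, or 2.1 to 5.6 points over the same SD range, so a shift of 0.23 SD is below one standard error. That is fair context, although the usual confidence interval makes no allowance for such a bias. The lower SD of 5.7 also rests on assumed correlations and on a cut-off applied at screening, while FSS is repeated at the baseline visit and may vary more there.

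Lastly, scores taken after steroids or new medication are affected by them, and other pre-specified strategies could be defended. That bears on which analysis is primary. Collecting the scores keeps the choice open, since uncollected scores cannot be recovered.

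**Conclusion.** The concern holds and should be fixed. Followed as written, the plan leaves any patient withdrawn in the first six weeks without the primary score, for reasons that may be related to fatigue, and the intention-to-treat analysis cannot be carried out for that patient.

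The gap in the text is certain; its effect on the result is not. The direction is undetermined and the frequency may be zero. The illustrated shift for two losses from one arm runs from nothing (loss unrelated to response) through 0.7 to 1.9 points (two of the worst seven) to 1.3 to 3.5 points (the two worst), against a hypothesised difference of 10 points. These figures rest on the assumed SD of change, normality and one-sided loss. The precision loss from two patients is small, at about 3 percentage points of power.

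**What to change.** Reconcile Sections III, V and VI:

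- **Section III:** state that these events do not end outcome follow-up. Whether light therapy continues afterwards is for the sponsor to state; no clinical rule is proposed here.
- **Section V:** collect the end-of-treatment FSS at its scheduled time, and the post-wash-out FSS, from every randomised patient who still agrees. Use the REDCap email survey when no visit takes place, and record how each score was collected.
- **Section VI:** analyse all randomised patients as assigned, including scores taken after an event. Name one method for FSS that is still missing; a likelihood-based model or multiple imputation would each be acceptable. Add a simple sensitivity analysis, such as counting missing changes as no improvement, read as a rough check because single imputation understates uncertainty. Add a second one that excludes post-event scores. Report the number, trigger and timing of events by arm.

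The cost is a sentence or two in each section and a survey link for the patients concerned. There are two drawbacks. Post-event scores may be shifted by steroids or new medication, which can dilute or bias the light effect if events differ between arms. Some primary scores would also come by email rather than in person. The analysis without post-event scores and the record of collection mode let readers judge both.
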